**LIST OF ABBREVIATIONS**

ABBREVIATION	DEFINITION
BGM	Blood Glucose Meter
CDC	Centers for Disease Control and Prevention
CDCES	Certified Diabetes Care and Education Specialist
CFR	Code of Federal Regulations
CGM	Continuous Glucose Monitor
DKA	Diabetic Ketoacidosis
FDA	Food and Drug Administration
GCP	Good Clinical Practice
HbA1c	Hemoglobin A1c
IRB	Institutional Review Board
MDI	Multiple Daily Injections
SH	Severe Hypoglycemia
T1D	Type 1 Diabetes
T2D	Type 2 Diabetes

## PROTOCOL SUMMARY

PARTICIPANT AREA	DESCRIPTION
Title	Virtual Diabetes Specialty Clinic: A Study Evaluating Remote Initiation of Continuous Glucose Monitoring
Précis	This study will assess feasibility and efficacy of establishing a virtual diabetes clinic with a focus on introduction of CGM technology and ongoing CGM use to minimize such rate-limiting factors as geography, cost and access to specialty care
Objectives	The objective of this study is to evaluate a virtual diabetes clinic model, for adults with either T1D or T2D, that supports integration of CGM into diabetes self-management and evaluates use of decision support technology within the virtual clinic model.
Study Design	Single-arm prospective longitudinal study
Eligibility Criteria	
Inclusion Criteria
 
 
• Age <math>\geq</math>18 years old
 
• Diagnosis of type 1 diabetes or type 2 diabetes and using insulin therapy (at least 3 injections of insulin per day or insulin pump that is compatible with Tidepool software) Multiple daily injection (MDI) users must be willing to use a device provided by the study that records the injection dosages and/or enter insulin dosing information through an app
 
• See a healthcare provider at least once a year
 
• Resident of United States and plan to reside in the U.S. for the duration of the study *This requirement is due to virtual clinic license requirements and U.S. use restrictions for some study software and devices. Not all U.S. states may be eligible for inclusion due to virtual clinic license status.
 
• Use either an Android or iOS smartphone that is compatible with app requirements that are needed for the study
 
• Access to a compatible computer with internet
 
• Understand written and spoken English
 
• Willing and able to follow the study procedures as instructed
 
 
Exclusion Criteria
 
 
• Current use of a closed loop system where an insulin pump and CGM share information and insulin dose is automatically adjusted based on glucose reading
 
• Current CGM use where Time in Range is <math>\geq</math>60% or Time <math><</math>54% <math>\leq</math>1.0%).
 
• Current use of any off-label glucose-lowering medications for diabetes type (Example: T1D use of non-insulin, anti-diabetic medications including SGLT2 inhibitors) *Use of such medications during the study will also be prohibited.
 
• Females who are pregnant, intending to become pregnant, or breastfeeding during the study
 
• Current renal dialysis or plan to begin renal dialysis during the study
 
• Active cancer treatment
 
• Extreme visual or hearing impairment that would impair ability to use real-time CGM
 
• Known adhesive allergy/prior skin reaction or skin reaction identified during the blinded CGM use phase that would preclude continued CGM use
 
• Participation in a different diabetes management study during the study
 

PARTICIPANT AREA	DESCRIPTION
	
 
Planned relocation to a state other than current state of residence during the study if virtual clinic is not licensed in the new state. Individuals working routinely in a state other than current state of residence in the next six months are also ineligible if the virtual clinic is not licensed in that state.
 

Sample Size	The recruitment target is 300 initiating CGM.
Outcomes	
Efficacy Outcomes: CGM use; CGM metrics for hypoglycemia (<54 and <70 mg/dL), hyperglycemia (>180 and >250 mg/dL), time in range (70-180 mg/dL), mean glucose, and glycemic variability (coefficient of variation); HbA1c; participant- reported outcomes including psychosocial and diabetes treatment satisfaction questionnaires
 
Safety Outcomes: Severe hypoglycemia, diabetic ketoacidosis, hospitalizations, and emergency room visits

Participant Duration	Study participation will be up to 12 months.
Protocol Overview/Synopsis	
Patient Population Adults ≥ 18 years with type 1 diabetes or type 2 diabetes using insulin therapy will be enrolled. Although the primary focus of the study is to enroll non-CGM users, CGM users whose glycemic control is suboptimal can be enrolled. Potential participants may be recruited through insurance providers, primary care networks, or health care providers.
 
Baseline Data Collection Baseline data collected will include demographics, height and weight, socioeconomic status, diabetes history, knowledge of and experience with diabetes devices, medical history and medications, and health-related physical activity. Questionnaires will collect information related to hypoglycemia awareness, treatment satisfaction, and psychosocial issues. Participant contact information will be collected. Contact information for the participant's diabetes healthcare provider will also be collected.
 
HbA1c Participant will receive fingerstick HbA1c kits that will be sent to a central lab for measurement after enrollment and at 13 weeks, 26 weeks, 39 weeks, and 52 weeks.
 
Contact between Study Team and Participant Each participant will be assigned to work with virtual clinic team members. Mental health service support options for diabetes-related mental health issues will be discussed as needed.
 
Virtual clinic team members will check in with participants during the initial six months of study follow up to review CGM data and recommendations related to diabetes management. Participants who continue in the optional extended follow-up phase after the first six months can contact the virtual clinic as needed.
 
CGM Use Participants who do not currently use a CGM will use a blinded CGM device for a single sensor wear period prior to CGM initiation. Participants may be asked to use a blinded CGM for an additional sensor wear period(s) if enough CGM data are not available to establish a baseline that can be used as baseline comparator data. Current CGM users will be asked to share their CGM data to confirm that they meet study eligibility criteria and to establish a baseline that can be used as baseline comparator data. Virtual training will include CGM set up, sensor insertion, alerts and alarms, uploading data, and visualizing data.
 
Changes in Insulin Dosing

JAEB CENTER FOR HEALTH RESEARCH

PARTICIPANT AREA	DESCRIPTION
	If the virtual clinic team believes that changes in insulin type or dosing should be considered, they will work with the participant to implement any such changes. Decision support tools, which include use of a mobile application, may be used if available to provide the virtual clinic team with potential recommendations regarding insulin use.

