139 consent for follow up after the first 6 months if they plan to continue use of CGM.

140 **2.2 Participant Inclusion Criteria**

141 Individuals must meet all the following inclusion criteria in order to be eligible to participate in  
142 the study:

- 143 1. Age  $\geq 18$  years old
- 144 2. Diagnosis of type 1 diabetes or type 2 diabetes and using insulin therapy (at least 3 injections  
145 of insulin per day or insulin pump that is compatible with Tidepool software)  
*146 Multiple daily injection (MDI) users must be willing to enter insulin dosing information  
147 through an app*
- 148 3. See a healthcare provider at least once a year
- 149 4. Resident of United States and plan to reside in the U.S. for the duration of the study  
*150 This requirement is due to virtual clinic license requirements and U.S. use restrictions for  
151 some study software and devices. Not all U.S. states may be eligible for inclusion due to  
152 virtual clinic license status.*

153 5. Use either an Android or iOS smartphone that is compatible with app requirements that are  
154 needed for the study  
155 6. Access to a compatible computer with internet  
156 7. Understand written and spoken English  
157 8. Willing and able to follow the study procedures as instructed

158 **2.3 Participant Exclusion Criteria**

159 Individuals meeting any of the following exclusion criteria at baseline will be excluded from  
160 study participation:

161 1. Current use of a closed loop system where an insulin pump and CGM share information and  
162 insulin dose is automatically adjusted based on glucose reading  
163 2. Current CGM use where Time in Range is  $\geq 60.0\%$  or Time  $< 54\%$  is  $\leq 1.0\%$ .  
164 3. Current use of any off-label glucose-lowering medications for diabetes type (Example: T1D  
165 use of non-insulin, anti-diabetic medications including SGLT2 inhibitors)  
166 *Use of such medications during the study will also be prohibited.*  
167 4. Females who are pregnant, intending to become pregnant, or breastfeeding during the study  
168 5. Current renal dialysis or plan to begin renal dialysis during the study  
169 6. Active cancer treatment  
170 7. Extreme visual or hearing impairment that would impair ability to use real-time CGM  
171 8. Known adhesive allergy/prior skin reaction or skin reaction identified during the blinded  
172 CGM use phase that would preclude continued CGM use  

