212 Other sensors that become FDA approved during the course of the study may be included as an  
213 option for participants. If additional sensors are included, the participants will be given  
214 information about CGM system options and will review the CGM systems with a study team  
215 member. A recommendation may be provided for one of the systems based on discussion with  
216 the participant, or there may be an indication that there is no specific recommendation.  
217 Participants will be able to select the CGM system that they prefer, regardless of  
218 recommendation. After a CGM system is selected, the participant may be asked why that system  
219 was selected.

220 **2.7 Blinded CGM**

221 Non-CGM users will use a blinded CGM device for a single sensor wear period (usually at least  
222 10 days) prior to CGM initiation. Current CGM users will be asked to use a blinded CGM device  
223 for a single sensor wear period if their current CGM data cannot be successfully shared to  
224 confirm eligibility. Study supplies required for blinded CGM data collection will be sent to the  
225 participant by mail. An Android phone may be provided which is used as a receiver to collect  
226 data from the blinded Dexcom G6 Pro. Current non-Dexcom CGM users, including pump users  
227 with integrated CGM should continue to use their personal CGM for glucose management.

228 A virtual clinic team member will be available to answer questions about blinded CGM use. The  
229 participants will not be able to see the glucose values and will be expected to follow their normal  
230 diabetes management practice during this blinded CGM use period. The goal will be to obtain  
231 ten days of blinded data. Participants may be asked to use a blinded CGM for an additional  
232 sensor wear period if enough CGM data are not available to establish baseline comparator data.  
233 Participants will be dropped from the study if blinded data cannot be obtained. Participants who  
234 have a serious skin reaction to the sensor during blinded CGM wear that precludes continued use  
235 of a sensor will be dropped. If additional FDA-approved CGM options are available for use in  
236 this study, the participant may be offered the opportunity to try the other CGM system; in this  
237 case blinded data collection would be repeated with another system.

238 **2.8 Psychosocial Screening Questionnaires**

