#### 430      Efficacy Outcomes:

- 431      • HbA1c
- 432      • CGM use
- 433      • Mean of sensor glucose levels
- 434      • Percentage of time spent with sensor glucose levels <54 and <70 mg/dL
- 435      • Percentage of time spent with sensor glucose levels >180 and >250 mg/dL
- 436      • Percentage of time spent with sensor glucose levels in the target range (70-180 mg/dL)
- 437      • Glycemic variability measured by the coefficient of variation
- 438      • Insulin metrics
- 439      • Questionnaire scores (and their corresponding subscales)
- 440      • Psychosocial metrics
- 441      • Healthcare utilization metrics

442      CGM, HbA1c, and questionnaires outcomes will be evaluated at all time points they are  
443      collected.

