Virtual Diabetes Specialty Clinic: A Study Evaluating Remote Initiation of Continuous Glucose Monitoring

VDiSC Study

Statistical Analysis Plan

Version: 1.0

Version Date: 12/30/2020

Author: [name]

Based on Protocol Version: 2.0

Note: The table shells are included in a separate document.

Revision History

The following table outlines changes made to the Statistical Analysis Plan.

Version Number	Author	Approver	Effective Date	Study Stage
1.0	[name]	[name]	12/30/2020	Study Enrollment

Version Number	Revision Description

Approvals

Role	Digital Signature or Handwritten Signature/Date
Author: [name]	
Senior Statistician: [name]	
JCHR Sponsor Representative: [name]	

1 **1 Statistical and Analytical Plans**

2 This document summarizes the proposed analyses to be performed for the Virtual Diabetes
3 Specialty Clinic (VDiSC) study. All analyses are exploratory and additional analyses and
4 outcomes not pre-specified here may be performed in the future. The table shells detailing how
5 the results will be displayed will be shown in a separate document.

6

7 **2 Study Overview**

8

9 The following two tables gives an overview of the VDiSC study.

10 **Table 1. Study Overview**

PARTICIPANT AREA	DESCRIPTION
Title	Virtual Diabetes Specialty Clinic: A Study Evaluating Remote Initiation of Continuous Glucose Monitoring
Précis	This study will assess feasibility and efficacy of establishing a virtual diabetes clinic with a focus on introduction of CGM technology and ongoing CGM use to minimize such rate-limiting factors as geography, cost and access to specialty care
Objectives	The objective of this study is to evaluate a virtual diabetes clinic model, for adults with either T1D or T2D, that supports integration of CGM into diabetes self-management and use of decision support technology.
Study Design	Single-arm prospective longitudinal study

PARTICIPANT AREA	DESCRIPTION

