Eligibility Criteria	
Inclusion Criteria
 
 • Age ≥ 18 years old • Diagnosis of type 1 diabetes or type 2 diabetes and using insulin therapy (at least 3 injections of insulin per day or insulin pump that is compatible with Tidepool software) Multiple daily injection (MDI) users must be willing to use a device provided by the study that records the injection dosages and/or enter insulin dosing information through an app • See a healthcare provider at least once a year • Resident of United States and plan to reside in the U.S. for the duration of the study This requirement is due to virtual clinic license requirements and U.S. use restrictions for some study software and devices. Not all U.S. states may be eligible for inclusion due to virtual clinic license status. • Use either an Android or iOS smartphone that is compatible with app requirements that are needed for the study • Access to a compatible computer with internet • Understand written and spoken English • Willing and able to follow the study procedures as instructed 
Exclusion Criteria
 
 • Use of real-time CGM (including Abbott Libre or integrated pump system) in last 12 months (interval blinded CGM use is acceptable) • Current use of any off-label glucose-lowering medications for diabetes type (Example: T1D use of non-insulin, anti-diabetic medications including SGLT2 inhibitors) Use of such medications during the study will also be prohibited. • Females who are pregnant, intending to become pregnant, or breastfeeding during the study • Current renal dialysis or plan to begin renal dialysis during the study • Active cancer treatment • Extreme visual or hearing impairment that would impair ability to use real-time CGM • Known adhesive allergy/prior skin reaction or skin reaction identified during the blinded CGM use phase that would preclude continued CGM use • Participation in a different diabetes management study during the study • Planned relocation to a state other than current state of residence during the study if virtual clinic is not licensed in the new state. Individuals working routinely in a state other than current state of residence in the next six months are also ineligible if the virtual clinic is not licensed in that state.
Sample Size	The recruitment target is 300 initiating CGM.

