- 59 • HbA1c, questionnaires, insulin, and other analyses will include all subjects with any
 60 amount of corresponding data following CGM initiation.
- 61 • The tabulations of the safety outcomes will include all participants who enrolled,
 62 regardless of how much data is available.

63 **7 Analysis of Study Endpoints**

64 **7.1 Calculation of CGM Metrics**

65 **7.1.1 Calculation of 13 Week CGM Metrics**

66 All CGM metrics listed in Section 5 will be calculated on a 13-week period for each subject
 67 level. The windows for the 13-week periods are defined as follows:

Time Point	Window
1-13 Weeks	0 to 91 days after the CGM initiation date
14-26 Weeks	92 to 183 days after the CGM initiation date
27-39 Weeks	184 to 274 days after the CGM initiation date
40-52 Weeks	275 to 365 days after the CGM initiation date

68
 69 For each 13-week period, CGM metrics will be calculated by pooling all CGM readings
 70 occurring from 12:00 AM on the first day of the 13-week period up until 11:59PM on the last
 71 day of the 13-week period. For the first 13-week period, the first CGM reading will be the start
 72 datetime of the period. If a participant discontinues CGM prior to the last day of the 13-week
 73 period, then CGM data will include readings up to the last CGM reading on the discontinuation
 74 date. Calibrations will be excluded from all these calculations. CGM metrics for 13-week periods
 75 with less than 168 hours of CGM data will be set to missing.

76 Baseline CGM metrics will be calculated by pooling all blinded CGM readings up to 90 days
77 prior to the date of CGM initiation for each subject. Baseline CGM metrics with less than 72
78 hours of CGM data will be set to missing.

79 The amount of time using the CGM will be calculated as the number of CGM values multiplied
80 by the expected CGM measurement frequency (i.e., 5min in general), with the exception that
81 there can only be one value within the CGM measurement frequency. Percentage of time CGM
82 is used will be calculated as the amount of time using the CGM divided by the total possible time
83 the participant could have used the CGM during the same period. Note that this denominator
84 includes sensor warm-up periods with no CGM values, so this metric will serve as a conservative
85 estimate of CGM use.

86 **7.1.2 Calculation of 4 Week CGM Metrics**

87 All CGM metrics listed in Section 5 also will be calculated on a 4-week interval for each subject.

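### Current CGM users are selected on poor glucose metrics and the same readings become their baseline, so part of their gain in time in range is regression to the mean

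*Protocol*

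**What the plan says.** The Protocol Summary makes non-users the main focus but adds that "CGM users whose glycemic control is suboptimal can be enrolled". Exclusion 2 in Protocol 2.3, which begins "Current CGM use where Time in Range is", removes a current user whose time in range is at least 60.0% or whose time <54 is at most 1.0%.

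For users who pass, the CGM Use paragraph of the synopsis states: "Current CGM users will be asked to share their CGM data to confirm that they meet study eligibility criteria and to establish a baseline". Protocol 2.7 asks the others to wear a blinded sensor "for a single sensor wear period if their current CGM data cannot be successfully shared to" confirm eligibility. A footnote to the Schedule of Study Visits says that this wear also sets their baseline.

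Both selection metrics are efficacy outcomes in Protocol 6.3, for example "Percentage of time spent with sensor glucose levels in the target range (70-180 mg/dL"). The design is single-arm. Protocol 6.5 and SAP 7.4 test mean change from baseline against zero, and SAP 3 stratifies by diabetes type only.

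The SAP is marked "Based on Protocol Version: 2.0". Its Table 1 still excludes "Use of real-time CGM (including Abbott Libre or integrated pump system) in last 12 months", and SAP 7.1.1 defines baseline from blinded data only: "Baseline CGM metrics will be calculated by pooling all blinded CGM readings up to 90 days" before initiation, with a 72-hour minimum.

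**The concern.** A person admitted because one stretch of readings was poor will, on average, look better in the next stretch even if nothing changes. If the poor stretch is also the baseline, that rebound counts as improvement, and a single-arm design has no control group to subtract it. Non-users face no glucose threshold at entry, so they do not carry this artefact. A result for current users, or any estimate that mixes them with non-users, would lean toward benefit. The reader could not see by how much, because CGM use at entry is neither a stratum nor a subgroup factor in SAP 12.

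**Working it through.** **No plan figure to reproduce.** The target of 300 is a convenience sample. The documents give no SD, reliability, length of shared data or number of current users.

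**Inputs.** From the documents: the 60% and 1.0% thresholds, one arm, and a test against zero. Time <54 in the exclusion is read as the percentage of time below 54 mg/dL. Assumed: time in range among current users has mean 60 and SD 18; time <54 is log-normal with median 0.4% and log-SD 1.2; the two metrics are uncorrelated; the eligibility and baseline windows are identical; there is no true change.

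**Time in range, both metrics must be poor** (the literal reading: being good on either one excludes). With window-to-window reliability ρ and a = (60 − mean)/SD:

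spurious gain = (1 − ρ) × SD × φ(a)/Φ(a)

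Here a = 0, so SD × φ/Φ = 18 × 0.3989/0.5 = 14.36.

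**Time in range, either poor metric suffices.** Let q be the chance that time <54 is at most 1.0%: q = Φ(ln(1.0/0.4)/1.2) = Φ(0.764) = 0.777. Then:

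spurious gain = (1 − ρ) × SD × φ(a) × q / [1 − (1 − Φ(a)) × q]

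The multiplier of (1 − ρ) is 18 × 0.3989 × 0.777 / (1 − 0.5 × 0.777) = 9.13.

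| Reliability ρ | Both required (points) | Either suffices (points) |
|---|---|---|
| 0.95 | 0.7 | 0.5 |
| 0.90 | 1.4 | 0.9 |
| 0.80 | 2.9 | 1.8 |
| 0.70 | 4.3 | 2.7 |

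**Time <54 mg/dL**, by simulation under the same assumptions:

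| Reliability (log scale) | Median, both required | Median, either suffices |
|---|---|---|
| 0.80 | 1.73% to 1.41% | 0.56% to 0.52% |
| 0.65 | 1.73% to 1.12% | 0.56% to 0.49% |
| 0.50 | 1.73% to 0.89% | 0.56% to 0.47% |

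If both are required, 34%, 45% and 54% of these users return to 1.0% or below with no intervention.

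**Other assumptions.** A second simulation used mean 55, SD 17, median time <54 of 0.3%, log-SD 1.3, correlation between the metrics of −0.3 to +0.3, and time-in-range reliability of 0.70 to 0.95. Time in range rose by 0.2 to 4.7 points (both required) or 0.3 to 2.7 (either). Mean time <54 fell by 0.16 to 1.05 points (both) or 0.02 to 0.10 (either). With an assumed 40 current users, a nominal 5% test of time in range was significant in 6% to 66% of null trials (both) or 7% to 28% (either).

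**Separate baseline window.** In that simulation, taking baseline from a different window with independent errors left a spurious change within 0.05 points of time in range and 0.02 points of time <54.

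**Dilution.** Pooled artefact = share of current users × their artefact. For a 4-point artefact, a 10% share gives 0.10 × 4 = 0.4 points and a 30% share gives 0.30 × 4 = 1.2.

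**The case against.** The strongest reply is that the SAP does not foresee these participants. It excludes recent real-time CGM users and takes baseline from blinded readings only, so users who share data have no SAP baseline at all. This stands. A reader might infer that the SAP deliberately pools current users with non-users; it does not say so. Pooling is what follows if the present stratification is applied unchanged.

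Second, full overlap is assumed. The protocol gives no window for either purpose and allows extra blinded wear. If the SAP's 90-day look-back were extended to shared data, readings after screening would enter the baseline and shrink the artefact. This also stands: the figures above are for full overlap.

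Third, every analysis is exploratory and there is no primary outcome. A reader might infer that a headline result is compromised, or that the study sets out to establish benefit in current users. Neither is supported: the remark that such users may benefit is background in Protocol 1.1, not part of the objective. Exploratory status does not remove the bias, however, and SAP 7.4 still plans tests, point estimates and 95% confidence intervals for glycemic change.

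Fourth, a later baseline is not perfectly clean. The schedule places first virtual-clinic contact and tutorials before baseline CGM collection, so post-eligibility readings may already reflect some intervention.

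**Conclusion.** The concern holds for current CGM users. The protocol selects them on two outcome metrics, reuses the selecting data as baseline and has no control arm. Part of their apparent gain in time in range will be regression to the mean, by about 0.5 to 4.3 points for reliability 0.95 to 0.70, given the assumed distributions, uncorrelated metrics and full overlap.

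A large spurious fall in time <54 mg/dL is tempting to claim as well. It follows only if exceeding that threshold is required for entry, as the exclusion literally reads; if either poor metric suffices, it is near zero. Nor can a material bias in the overall results be claimed, since the share of current users is not stated and non-users are the main focus. Separately, protocol and SAP disagree on who is enrolled and what the CGM baseline is, and must be reconciled.

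**What to change.** When the SAP is brought into line with the current protocol:

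1. Report CGM change from baseline separately for non-users and current CGM users within diabetes type, and add a sensitivity analysis that drops current users from pooled estimates. This needs only data already being collected and keeps the non-user results free of the artefact.
2. Define a CGM baseline for current users. Where readings exist after the eligibility window and before study CGM initiation, use those, with at least 72 hours as in SAP 7.1.1, and note that they may follow first virtual-clinic contact. Otherwise, label the current-user change as subject to regression to the mean.
3. Reconcile the wording of the time-in-range / time <54 exclusion in the Protocol Summary and Protocol 2.3 with its intent, so that it is clear whether one or both metrics must be poor.

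The cost is document wording, one more table stratum, less precision in the smaller groups, and a shorter baseline for some current users. Some of them may also have to share data a second time.
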